There is promising early evidence that Baby CHAT is acceptable to participants and has the potential to improve prenatal bonding and RF in a non-clinical sample of expecting parents (Cox et al., 2020). Given these encouraging findings, the present study aims to examine the acceptability and feasibility of this intervention with a sample of pregnant women with depression, who are more likely to experience difficulties with bonding and RF. As Baby CHAT is a novel intervention, the study will also examine the feasibility of conducting research with Baby CHAT with this population.

Terminology

In the interests of brevity, the term 'pregnant women' will be used in the rest of this protocol to refer to all pregnant/birthing people, including women, non-binary people and transgender men, who will all be eligible to participate in this study.

2 Study Objectives and Design

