2.1. Study Objectives

The primary objective of the study is as follows:

- To assess the acceptability and feasibility of a single-session psychoeducational group intervention, Baby CHAT, in women experiencing mild-to-moderate depression during pregnancy

Further, secondary objectives, are:

- To provide preliminary evidence for Baby CHAT's effect on parental RF and prenatal bonding in pregnant women with depression
- To further develop the intervention from participants' feedback and running of the group

The study's primary end point is as follows:

- The study will be completed once Baby CHAT has been run enough times for 24 participants to attend and the last participant has completed their outcome questionnaires 1 month after attending the final group

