2.2 Study Design & Flowchart

Baby CHAT is a novel intervention and, to our knowledge, has never been trialled with pregnant women with depression. Therefore, a feasibility design is appropriate to explore whether Baby CHAT is acceptable to participants, if they experience the intervention as helpful, and to understand whether it is possible to recruit for and complete research on Baby CHAT with this group. Feasibility studies vary in scope but include assessing how practical it is to deliver the intervention, what the demand for the intervention is and how participants respond to it (Bowen et al., 2009). The findings of feasibility studies can then inform subsequent, larger-scale trials on the efficacy of the intervention.

A single-arm repeated measures mixed-methods design will be utilised to provide rich feedback on the acceptability and feasibility of Baby CHAT. The aims of the quantitative arm of the study will be to gather descriptive statistics on the feasibility of the intervention, including uptake and retention of participants and whether the intervention can feasibly be delivered during the given time frame. Effect sizes will also be calculated to inform sample size calculations for a larger-scale clinical trial in the future.

The qualitative arm of the study will gain participants' feedback on the content and impact of the intervention, including their opinions on use of the 4D scan footage, level of adaptation for low mood and any suggested improvements. This qualitative data will provide rich information about participant's experiences of Baby CHAT, that will inform the next stage of the intervention's development.

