2.3 Study Flowchart

	Screening	Baseline	Intervention	Post-intervention	1-month follow-up
Written informed consent	X				
Demographics	X				
EPDS	X			X	X
MAAS		X		X	X
P-PRFQ		X		X	X
Baby CHAT intervention			X		
Feedback form				X	
Adverse events				X	

3. Sample Size, Statistics, Selection and Withdrawal of Subjects

Sample size

This study is concerned with generating descriptive statistics to assess the feasibility of the proposed methods, rather than establishing effectiveness or generalisability of the intervention. There has been disagreement in the literature on appropriate sample sizes for feasibility studies, but sample sizes between 24 and 50 have been recommended (Lancaster, Dodd & Williamson, 2004; Sim & Lewis, 2012; Julious, 2005). To further aid decision-making regarding an appropriate sample size for the current project, sample sizes of similar studies in the field were also reviewed. These included N=24 in the treatment arm for the intervention Nurture and Play (Salo et al., 2019), and N=25 for a feasibility trial of the Beating the Blues Before Birth intervention (Milgrom et al., 2015).

In qualitative studies, there is often less rigour in the choice and justification of the sample sizes used (Marshall et al., 2013). Qualitative research often concerns developing a depth of understanding, and therefore data saturation, that is, the point at which including more participants no longer contributes additional perspectives, is often suggested as a guide for ending recruitment (Glaser & Strauss, 1967). However, this provides little guidance for estimating sample sizes prior to data collection. Determination of appropriate sample sizes in advance will depend on the context and scientific paradigm of the research (Boddy, 2016). This study involves a brief qualitative component designed to generate a breadth of feedback on the intervention. Meanwhile, it is feasible to ask all participants to provide qualitative feedback, using the questionnaire following completion of the intervention.

Taken together, a sample size of N=24 is estimated as appropriate for both the quantitative and qualitative components of the study. This is expected to be achievable based on current recruitment rates in a similar study with women with prenatal depression (the DAWN trial; Trevillion et al., 2020) and given that in 2020, around 925 babies were born in Southwark, Lambeth and Lewisham each month (Office for National Statistics, 2020).

Participant selection

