An opportunity sample of participants will be recruited through their clinician or self-referral. This study will recruit participants from South London and Maudsley NHS Foundation Trust (SLaM) who are receiving care within the primary care Improving Access to Psychological Therapies (IAPT) services and secondary care perinatal services in Lambeth, Southwark, Lewisham and Croydon. The student researcher will have no prior relationship with the participants. The research team will share information with clinicians about Baby CHAT and the study procedures, so that they have a good understanding of the study before they are asked to give their patients information about the research. Clinicians will provide eligible clients with a flyer (see Appendix 2 for flyer) and, if a client is interested, will ask for verbal consent for the student researcher to contact them by phone (just name and phone number provided at this stage). To enable self-referral, posters will be placed in the waiting areas of relevant services. Posters will also be placed in maternity scanning clinics at King's College Hospital and St Thomas' Hospital, for participants to self-refer. The study will also be advertised through carefully selected online groups, social media channels and the King's College London research participation email circular.

Once a potential participant has self-referred or consented to be contacted via their clinician, the student researcher will contact them to check eligibility, introduce the project, provide the information sheet and to answer any questions. Participants will have sufficient time to consider whether they consent to take part. Participants will be offered £20 in reimbursement for taking part in the study.

Inclusion criteria

Participants eligible to take part in the project will be women aged ≥ 18 years who are pregnant, between 20- and 34-weeks' gestation, and currently experiencing depressive symptoms as identified by the EPDS. Those scoring >13 will be eligible to take part in the study. Both first-time and experienced parents will be eligible to participate.

Given the study involves the participation of potentially vulnerable individuals, all participants must be resident in or accessing services in a London borough served by SLaM, in order to facilitate access to local mental health services if needed.

Exclusion criteria

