Although this study is exploratory due to the novelty of the intervention, within feasibility research it is appropriate to set a priori thresholds for the main feasibility and acceptability outcomes. Feasibility thresholds will be as follows: 30 or more potential participants express interest in the study (participant uptake); 20 or more participants attend Baby CHAT (participant retention); and at least 70% of participants complete the study measures (missing data). The acceptability of Baby CHAT will be assessed by the feedback form, which consists mostly of open-ended questions. These will be analysed qualitatively and therefore no specific acceptability thresholds will be set.

Effect sizes for primary and secondary outcome measures will be calculated using Cohen's d. These effect sizes will inform the sample size calculations of future larger-scale studies on Baby CHAT.

Items on the outcome questionnaires will be designated as mandatory on the online survey portal, Qualtrics, to minimise missing data. Participants will be contacted to attempt to complete any missing items from other forms. Therefore, no statistical imputation methods will be required to correct for missing data.

Any deviations from the original statistical analysis plan will be reported in a protocol amendment.

4. Study procedures

Informed consent procedure

All interested participants, whether they self-referred to the study or consented to be contacted via their clinician, will have an initial contact with the research team to ask any questions about the project. Participants will be sent a full Participant Information Sheet by email to read and consider. The information in the Participant Information Sheet and opportunity for further discussion with the research team will allow detailed explanation of the aims, methods, anticipated benefits and potential harms of the study, as well as the participants' right to refuse involvement in the study and to withdraw consent at any time. The research team will ensure adequate time for each participant to consider their consent to take part. Individuals who agree to take part will then be asked to complete and return a signed consent form. All participants will receive a copy of their signed consent form.

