No significant changes will be made to the Baby CHAT group content for the purposes of this study. Baby CHAT was designed as a standalone session, that could be used as an add-on to existing treatments, and therefore does not target symptoms of depression specifically. However, the nature of the group discussions may naturally differ given that all participants will be experiencing depression during their pregnancy. Group facilitators will present the Baby CHAT content in a sensitive and non-blaming manner, validating participants' experiences. The facilitators will also sensitively facilitate discussions during the group around the group content, for example, anticipated difficulties engaging in new activities while experiencing depression.

While Baby CHAT was originally designed to be delivered face-to-face, in this study all sessions will be held virtually using video conferencing software. This will facilitate participants' access to the group and enable greater safety relating to the risk of Covid-19. Groups will be offered at a mixture of times, including weekdays and evenings.

End of study definition

The study will be considered completed once participants of the last Baby CHAT group have completed 1-month follow-up questionnaires. The REC will be informed once the study has ended.

6. Assessment of Safety

Adverse event reporting will take place following the intervention via the Baby CHAT feedback form. Participants will be asked if they experienced any negative effects from attending the group. These will be recorded and reported in the Annual Progress Report and copied to the sponsor.

SAEs are defined in this study as any adverse event which: results in death; is life-threatening; requires hospitalisation or prolongation of existing hospitalisation; results in persistent or significant disability or incapacity; or consists of a congenital anomaly or birth defect. SAEs are not anticipated to occur due to any of the study procedures. However, it is expected that SAEs may occur during the study for other reasons. Hospitalisation, likely due to complications with participants' pregnancies, will be considered an unrelated but expected SAE. Where SAEs are made known to the research team, these will be documented. Suspected unexpected serious adverse reactions (SUSARs) will be reported to the REC within 15 days of the Chief Investigator becoming aware.

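### Cohen's d from this single-arm study is to inform a later trial's sample size, but it is an uncontrolled and imprecise pre-post change, not a between-group effect

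*Combined protocol and SAP*

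**What the plan says.** Section 2.2 sets the design: "A single-arm repeated measures mixed-methods design will be utilised". It gives planning of a later trial as one reason for the quantitative work: "Effect sizes will also be calculated to inform sample size calculations for a larger-scale clinical trial in the future". Section 3 (Statistics) repeats this: "These effect sizes will inform the sample size calculations of future larger-scale studies on Baby CHAT". No other use for d is given there.

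Neither section states which time points d compares (Time 2 is within 48 hours of the group, Time 3 one month later), which SD it is divided by, whether it will carry an interval, or how change that would occur without Baby CHAT will be allowed for.

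Other statements that bear on the point:

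- Section 2.1 lists as a secondary objective preliminary evidence on Baby CHAT's "effect on parental RF and prenatal bonding in pregnant women with depression".
- Section 3 (Sample size) sets N=24 and describes the purpose as descriptive, "rather than establishing effectiveness or generalisability of the intervention".
- Section 3 (Participant selection) recruits women "who are receiving care within the primary care Improving Access to Psychological Therapies (IAPT) services and secondary care perinatal services", but also by self-referral through posters, online channels and an email circular. The exclusion section adds that some interested women may not be in treatment.
- Section 4 (Intervention) says that Baby CHAT "could be used as an add-on to existing treatments, and therefore does not target symptoms of depression specifically".
- Section 1 cites an earlier study suggesting that Baby CHAT "has the potential to improve prenatal bonding and RF in a non-clinical sample of expecting parents". The reference list titles it a randomised trial. Sections 2.2 and 3 do not say that its data, or any other controlled data, will be used for sizing.

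**The concern.** A comparative trial is sized on a difference between groups. A single-arm study yields a change within women. The two agree only if women without Baby CHAT would not change at all over the same interval. That is doubtful for bonding and reflective functioning measured while gestation advances, and for mood in women some of whom are receiving other care.

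If the observed d were carried forward as the target difference, all of that background change would be counted as effect. Sampling error comes on top: 24 women is the most expected, and the plan's own thresholds accept fewer. At stake is the size of the next trial. This study's feasibility and acceptability conclusions are not affected.

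**Working it through.** **Inputs from the documents.** One arm; N=24, chosen from published ranges and similar studies rather than from a formula, so there is no calculation to reproduce; withdrawals not replaced; thresholds of 20 attending and 70% completing. 70% of 24 is 16.8, so 17.

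**Assumed inputs.** Observed paired d (mean change / SD of change) of 0.50; later trial 1:1, two-sided 5%, 80% power; background change b; pre-post correlation r; equal SDs before and after and in both arms. None of these is in the documents.

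**1. Precision.** The interval for d uses the noncentral t distribution with t = d√n and n-1 degrees of freedom.

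| Women | 95% CI for d = 0.50 |
|---|---|
| 24 | 0.07 to 0.92 |
| 20 | 0.03 to 0.96 |
| 17 | -0.01 to 1.00 |

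**2. Background change, change-score analysis.** The normal approximation for the size per arm is 2(1.960 + 0.842)²/d² = 15.70/d². For d = 0.50 this is 62.8; the exact t calculation gives 64. If b of the observed 0.50 would have happened anyway, the between-group effect is 0.50 - b.

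| b | True effect | 15.70/d² | Exact n per arm | Power with 64 per arm |
|---|---|---|---|---|
| 0 | 0.50 | 62.8 | 64 | 80% |
| 0.10 | 0.40 | 98.1 | 100 | 61% |
| 0.20 | 0.30 | 174.4 | 176 | 39% |
| -0.10 | 0.60 | 43.6 | 45 | 92% |

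The last row is background change towards worsening, which leaves the trial larger than needed.

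**3. Baseline adjustment does not remove this.** The paired d converts as d√(2(1-r))/√(1-r²). At r = 0.7, 0.50 becomes 0.50 × 0.775/0.714 = 0.54, which needs 55 per arm. True effects of 0.40 and 0.30 need 85 and 150, and 55 per arm then gives 62% and 39% power.

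**4. Unstated standardiser, with no background change.** If the later trial compares unadjusted post scores, the relevant d is 0.50√(2(1-r)).

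| r | d for post scores | n per arm needed | n entered |
|---|---|---|---|
| 0.3 | 0.592 | 46 | 64 |
| 0.5 | 0.500 | 64 | 64 |
| 0.6 | 0.447 | 80 | 64 |
| 0.7 | 0.387 | 106 | 64 |
| 0.8 | 0.316 | 158 | 64 |

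The error undersizes above r = 0.5 and oversizes below it. A change-score analysis needs 64 at every r, and baseline adjustment needs 52, 55 or 58 at r = 0.6, 0.7 or 0.8, so neither is undersized.

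**5. EPDS pre value.** The Section 2.3 flowchart shows the EPDS before the intervention only at screening, where Section 3 requires a score above 13. Section 4 (Measures) names the EPDS as a secondary clinical outcome, and Section 4 (Study schedule) has women complete a baseline set of outcome questionnaires at Time 1 without listing them. That set may include the EPDS.

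If the screening score is the pre value, the expected drop with no effect is (1-r) × (mean of those selected - mean of the source population). Assume SD 5, r = 0.7 and selection above 13.5:

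- Source mean 13, no upper limit: the selected mean is 17.31, so the drop is 0.3 × 4.31 = 1.29 points, an apparent improvement.
- Source mean 16, upper limit 18.5: selection is symmetric about 16, so the drop is 0.
- Source mean 18, upper limit 18.5 or 20.5: the sign reverses, with d about -0.15 or -0.07.

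Section 3 excludes severe depression but gives no score for it, so the upper limits are assumptions too.

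**The case against.** The strongest reply is that the plan says only that d will inform later calculations, not that it will be the target difference. The study is labelled exploratory and disclaims effectiveness, and the later trial's design, analysis and error rates are unknown. That is fair: every size above is conditional and no result of this study changes. It does not meet the point, because sizing is the only use the Statistics section gives for d. No limit is placed on that use, and nothing commits the team to reporting what a later statistician would need to convert d.

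Four stronger readings are tempting, and the documents do not support them:

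- **All participants will be in other care.** Self-referral routes and the remark about women not in treatment mean this can be said only of some.
- **The EPDS change must be biased towards improvement.** Section 4 may already provide a Time 1 EPDS. If it does not, the exclusion of severe depression makes selection potentially two-sided, and zero or reversed bias is possible.
- **The unstated standardiser undersizes the later trial.** It does so only for unadjusted post scores with r above 0.5.
- **This protocol should fix where the later trial's target difference comes from.** That goes further than needed. The documents give no minimum important difference, and the cited earlier Baby CHAT study was in a non-clinical sample.

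**Conclusion.** The point holds. Sections 2.2 and 3 state a use for d that a single-arm study of 24 women cannot support unaided. The documents establish that each d will be an uncontrolled within-person change, with no stated contrast, standardiser or interval.

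How far a later trial would be mis-sized is not established. Under the assumed d of 0.50, background change of 0.10 or 0.20 towards improvement takes power at 64 per arm to 61% or 39%; change in the other direction makes the trial too large. A reader might infer that the later trial will be underpowered, but the documents fix neither the direction of background change nor the way d will be used.

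The standardiser and the EPDS pre value are minor. For the EPDS, regression to the mean may distort the change if the screening score is used, but its size and direction depend on the source population and on how severe depression is excluded, which the documents do not give. The plan should be changed, though the feasibility objectives do not depend on it.

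**What to change.** Replace the sentence in Section 3 (Statistics) and align Section 2.2 with:

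> Each d will be reported as an uncontrolled pre-post change with its time points, standardiser and 95% CI, together with the SDs and pre-post correlation. The SDs, correlation and the recruitment, attendance and completion rates will inform future sample size calculations; the single-arm d alone will not be used as the target between-group difference.

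The cost is revised wording and a few extra summary statistics. No participants, visits or control arm are added. The price is that a later team must support its target difference with something besides this d. The SDs need care as well: with 24 women, the 95% CI for an SD runs from about 0.78 to 1.40 times the estimate.

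Separately, reconcile the Section 2.3 flowchart with the baseline set in Section 4 (Study schedule) and state which EPDS score is the pre value. If it is the screening score, report the EPDS change with a note that selection on that score may distort it.

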Women will be excluded if they are experiencing severe depression or current severe co-morbid diagnoses (e.g. psychosis), if they endorse 'yes, quite often' or 'sometimes' on question ten of the EPDS (in the past 7 days, 'the thought of harming myself has occurred to me'), or if they are unable to complete informed consent and the questionnaires in English. Participants must be able to sufficiently understand the psychoeducational materials and group discussions during the intervention, so that all participants experience a 'high feedback', interactive intervention.

There will be clear signposting to NHS and third sector organisations (including the general practitioner, midwifery team, local psychological therapies service, and other online resources) for all included and excluded participants, given that women interested in the study will be experiencing subjective low mood and may not be accessing treatment.

Withdrawal of subjects

Participants have the right to withdraw from the study at any time for any reason. If participants drop out during the study their data will be included in the analysis, unless they also withdraw consent for this. No further data will be collected from them. Their pseudonymised data will be destroyed after a period of 5 years following completion of the study, consistent with Clinical Trials Regulations and in line with the rest of the data collected in this study. Efforts will be made to report reasons for withdrawal. Withdrawn participants will not be replaced. Withdrawn participants will receive signposting information to local mental health and other support services, as outlined above (see Exclusion criteria).

Statistics

The following quantitative feasibility and acceptability outcomes will be collected: rates of eligible participants, uptake and retention of participants, scores on the feedback form, rates of missing data, and scores on the fidelity checklist (to monitor intervention delivery). For the qualitative arm of the study, participants will complete the open-ended questions on the feedback form. Descriptive data on participant demographic characteristics will also be collected.

The quantitative feasibility and acceptability outcomes outlined above will be summarised descriptively. Qualitative data from the open-ended questions on the feedback form will be analysed using content analysis.

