Following informed consent, the depression screening measure (the EPDS) will be conducted. Participants will be informed in a timely and sensitive manner whether they have met the criteria

to be included in the study. Participants who consent but do not score above the threshold on the screening questionnaire will be signposted to appropriate sources of support (as above, see Exclusion criteria).

Study schedule

Following inclusion in the study (i.e. having completed informed consent and scored over the screening threshold), participants will be asked to complete the baseline set of outcome questionnaires via Qualtrics (Time 1). Once completed, the participant will be booked into an upcoming session of the Baby CHAT group.

Participants will attend an online Baby CHAT group at a time that is convenient for them. Up to eight women will be invited to each group, to facilitate optimal group dynamics and engagement with the group content. See below for further details of the intervention.

After attending Baby CHAT, participants will be asked to complete the post-intervention outcome questionnaires and feedback form within 48 hours of the group (Time 2). One month later, participants will be contacted to complete the final follow-up questionnaires (Time 3).

Measures

The primary clinical outcome will be prenatal bonding as measured using the Maternal Antenatal Attachment Scale (MAAS). Secondary clinical outcomes of RF and depressive symptomology will be measured using the Prenatal Parental Reflective Functioning Questionnaire (P-PRFQ) and the Edinburgh Postnatal Depression Scale (EPDS). Feedback forms, containing both qualitative and quantitative components, will also be administered after participants have attended Baby CHAT in order to gather feedback on experience of the intervention (including group format, content and perceived usefulness).

Edinburgh Postnatal Depression Scale

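### The only scheduled pre-group EPDS is the score used to select women (>13), so the EPDS Cohen's d will tend to show improvement through regression to the mean alone

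*Combined protocol and SAP*

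**What the plan says.** - **Design.** Section 2.2: "A single-arm repeated measures mixed-methods design will be utilised". There is no control arm.
- **Selection.** Section 3, Inclusion criteria: "Those scoring >13 will be eligible to take part in the study". Section 4, Screening procedure: "Following informed consent, the depression screening measure (the EPDS) will be conducted". Under Exclusion criteria: "Women will be excluded if they are experiencing severe depression or current severe co-morbid diagnoses"; no EPDS value is attached to severe depression.
- **Schedule.** The flowchart in 2.3 marks EPDS at Screening, Post-intervention and 1-month follow-up, with Baseline empty. MAAS and P-PRFQ are marked at Baseline, Post-intervention and 1-month follow-up. Section 4, Study schedule, says that after inclusion "participants will be asked to complete the baseline set of outcome questionnaires via Qualtrics (Time 1"), without naming the questionnaires.
- **Outcome and analysis.** Section 4, Measures: "Secondary clinical outcomes of RF and depressive symptomology will be measured using" the P-PRFQ and the EPDS. Section 3, Statistics: "Effect sizes for primary and secondary outcome measures will be calculated" as Cohen's d, and "These effect sizes will inform the sample size calculations of future larger-scale studies on Baby CHAT". Neither the contrast, the time point nor the standardising SD is given.

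No section mentions regression to the mean, a repeat pre-group EPDS or an adjustment.

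**The concern.** EPDS asks about the past week, so a woman's score varies between occasions. Taking only women whose score exceeds 13 favours those whose error on that day was upward. When they are measured again, the mean tends to fall even if nothing has happened. Truncation also narrows the spread of screening scores, which enlarges d further if the screening SD is the divisor. With one arm, nothing in the design separates this from benefit.

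The EPDS d could therefore be read as a mood benefit from a session that the Intervention section says is not aimed specifically at depressive symptoms. The follow-up feedback form (Appendix 6) asks whether the group helped mood, so such a reading is foreseeable.

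A related point covers all three scales: each d is an uncontrolled pre-post value. If carried into a later trial as a between-arm effect, it could mis-size that trial in either direction.

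**Working it through.** The plan gives no figure to reproduce. N=24 rests on cited ranges and similar studies, not on an effect size. The check asks what d would be expected if the group had no effect.

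**Inputs from the documents:** EPDS is a whole-number score on ten items of four levels (0 to 30), selection is >13 (14 or more), and there is one arm.

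**Assumptions, not in the documents:** source SD 5; retest correlation r of 0.7 to 0.8; mean among women screened varied from 9 to 18; no treatment effect or natural change.

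**Formulas (normal approximation).** With a = (13.5 − mean)/5 and λ = φ(a)/(1 − Φ(a)):
- expected fall = 5 × (1 − r) × λ
- screening SD after selection = 5 × √(1 − λ(λ − a))
- spurious d = fall / screening SD

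Worked case, mean 13 and r 0.7: a = 0.5/5 = 0.1 and λ = 0.863. The fall is 5 × 0.3 × 0.863 = 1.29. The SD is 5 × √(1 − 0.863 × 0.763) = 2.92. So d = 1.29/2.92 = 0.44.

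The last two columns come from simulation with scores rounded and limited to 0–30. The average SD is the mean of the screening and post-group SDs.

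| Source mean | r | λ | Fall, formula | Screening SD | d, formula | Fall, simulated | d, simulated: screening SD / average SD |
|---|---|---|---|---|---|---|---|
| 9 | 0.7 | 1.446 | 2.17 | 2.30 | 0.94 | 2.19 | 0.96 / 0.71 |
| 13 | 0.7 | 0.863 | 1.29 | 2.92 | 0.44 | 1.31 | 0.45 / 0.37 |
| 13 | 0.8 | 0.863 | 0.86 | 2.92 | 0.29 | 0.88 | 0.30 / 0.26 |
| 16 | 0.8 | 0.509 | 0.51 | 3.49 | 0.15 | 0.52 | 0.15 / 0.14 |
| 18 | 0.8 | 0.326 | 0.33 | 3.87 | 0.08 | 0.33 | 0.09 / 0.08 |

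**Upper cap.** The severe-depression exclusion may also truncate the top. With a purely illustrative cap of 20 and d on the screening SD:
- means 9 to 13: about 0.37 to 1.19
- mean 16: 0.09 to 0.14
- mean 17: about 0
- mean 18: −0.09 to −0.13

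The larger capped values at low means reflect a smaller divisor, not more regression. At mean 13 and r 0.7 the cap lowers the fall from 1.31 to 1.03 points. On the root-mean-square of the two SDs, the range for means 9 to 13 is 0.25 to 0.71.

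**Repeat EPDS at Time 1.** If screening and Time 1 errors correlate ρ and the post-group error is independent, the spurious fall from Time 1 is ρ times the fall from screening. Over the cells from mean 9, r 0.7 to mean 16, r 0.8, uncapped, with d on the Time 1 SD:
- ρ = 0: d about 0
- ρ = 0.5: falls of 0.5 × 2.19 = 1.10 and 0.5 × 0.52 = 0.26 points; d 0.33 and 0.07
- ρ = 0.9: falls of 1.97 and 0.47 points; d about 0.76 and 0.13

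A repeat completed almost together with screening would therefore achieve little.

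**Precision.** This uses a different divisor, the SD of the change, so it is not directly comparable with the values above. A standardised mean change of 0.5 has a 95% CI of 0.07 to 0.92 at n = 24. At 17 completers (70% of 24 is 16.8) it is −0.01 to 1.00.

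**The case against.** **The baseline wording may already include EPDS.** It is an outcome, and Time 1 is described as the set of outcome questionnaires. This stands as an ambiguity. But the text does not name EPDS there, and the flowchart, which does list measures by occasion, leaves that cell empty. If a repeat is intended, flowchart and text need reconciling and d must be tied to that score.

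**The stakes are limited.** The secondary objective on effect (2.1) names reflective functioning and bonding, not depression. The primary clinical outcome is MAAS. The sample-size section disclaims establishing effectiveness, and no feasibility threshold uses the EPDS d. All true, and it limits the priority. Even so, Statistics commits to a d for secondary outcomes and passes it to later sample sizes.

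**The size is driven by assumptions.** This also stands. Recruitment partly through psychological therapy and perinatal services may raise the source mean and shrink the bias. A tight severity cap could remove or reverse it, and the item-10 exclusion, a further selection on the same scale, was not modelled. On the other side, recruitment also uses posters, social media and a university email circular, and the Screening procedure provides for consenting women who do not exceed the threshold. A bias of unknown size, and possibly unknown sign, is itself a reason not to carry this d forward.

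**Conclusion.** The concern holds. Run as scheduled, the EPDS d compares later scores with the score on which women were selected, in a single arm, and will tend to show improvement without any effect of the group. Under the stated assumptions and no cap, source means of 9 to 16 give a fall of 0.5 to 2.2 points and a spurious d of 0.15 to 0.96 on the screening SD (0.14 to 0.71 on the average SD). At means of 17 to 18 it is 0.09 to 0.17. The direction could reverse only with a strict upper cap in a high-scoring source population.

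That the screening score serves as baseline is inferred from the flowchart. MAAS and P-PRFQ have their own baselines and are not selection variables, so they are affected only indirectly. This should be corrected, but it does not undermine the feasibility aims.

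**What to change.** 1. Mark EPDS at Baseline in the flowchart and name it in the Time 1 Qualtrics set. Collect it on a later occasion than screening, ideally more than 7 days after, so that the one-week recall periods do not overlap. Where that would delay a group, collect the ten items in the wait between booking and the session. Record the gap in days and compute EPDS change from this score.
2. State whether the Time 1 EPDS has any bearing on eligibility, and reconcile this and the handling of item-10 answers at Time 1 with the self-harm exclusion and the safeguarding pathway. The rule itself is for the investigators.
3. If a repeat is not possible, report EPDS change descriptively, without a d, and say why.
4. In Statistics, name the contrast and standardising SD for each d, give a 95% CI, and state that SDs and pre-post correlations, not the uncontrolled d, will inform the sample size of a controlled trial.

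**Cost.** Time 1 grows from 19 + 14 = 33 scale items to 43. These are the same three scales already given at Times 2 and 3, and the poster quotes about 10 minutes for each occasion. Because Time 1 currently precedes booking, collecting the items after booking adds one online contact and some chasing of non-completion. The rest is one flowchart mark and a few sentences. Natural remission and some residual regression to the mean will remain and should be acknowledged.
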